4.9. Blinding

The PREEMPT CRC study is a blinded study and follows blinding as per the study blinding plans. For this study, blinding is defined as preventing knowledge of subject-specific histopathological classifications or blood test results that could bias the study. Blood specimens were de-identified prior to being sent to Freenome for processing and storage. Specimen testing will be performed by laboratory personnel blinded to the results of the SOC screening colonoscopy. Subjects, their health care providers, and investigators will remain blinded to the results of FMBT-CRC.

To minimize risk of unintended unblinding at the time of data analysis, the study also maintained an unblinding plan which outline the Sponsor-level processes for unblinding specific roles/data, such as data preparation, data quality and control, and data analyses, as needed through

This document contains confidential, proprietary information and may not be reproduced or disclosed in whole or in part without written authorization from Freenome Holdings, Inc

		Approval Status	Approved
		Effective Date	5-Jan-2024
Document Number	PL-00052	Current Revision	5
Document Title	Clinical Validation of Freenome's Methylation Blood Test for the Early Detection...		
Document Category	Plan		

completion of this study (PL-00071). Unblinded roles are limited to a need-basis. Clinical Data Manager(s), Clinical Scientist(s), and Biostatisticians(s) can be unblinded if their defined responsibilities need to be conducted. Individuals granted access to unblinded data will not communicate results or characteristics of the unblinded data in any way that would expose information on subject-specific histopathological classifications (or any other blinded content) to individuals not granted access. Individuals granted access to the blinded data must not work on the classifier algorithms or have access to results of the blood test prior to study database lock. Individuals granted access to blinded data will be documented. The Sponsor will decide on the level of unblinding of PREEMPT CRC blinded data at the end of study.

4.10. Data Monitoring Committee

The DMC oversaw the PREEMPT CRC study and was responsible for:

- Determining the required number of events (e.g., evaluable subjects diagnosed with CRC) had been met to provide stopping guidance to Freenome.
- Monitoring data related to the quality of colonoscopies (specifically adenoma detection rate by gender, bowel preparation quality, and cecal intubation rate) to alert Freenome to sites or phlebotomists requiring remediation.
- Monitoring serious adverse events related to the study procedure (i.e., venipuncture for blood collection).

After the review of each Data Report was completed, the DMC Chairperson provided the official DMC recommendation to Freenome regarding the appropriateness of continuing the study, as well as any other recommendations relevant to study conduct and/or patient safety.

5. Analysis Populations

5.1. All Enrolled Subjects (ALL)

This set will include those subjects who enrolled (met eligibility criteria and consented).

This document contains confidential, proprietary information and may not be reproduced or disclosed in whole or in part without written authorization from Freenome Holdings, Inc

		Approval Status	Approved
		Effective Date	5-Jan-2024
Document Number	PL-00052	Current Revision	5
Document Title	Clinical Validation of Freenome's Methylation Blood Test for the Early Detection...		
Document Category	Plan		

5.2. Enrolled* Subjects (EN)

This set will include those subjects who enrolled on or after April 5, 2021, who met eligibility criteria and consented.

5.3. Full Analysis Set (FAS)

This set will include those subjects enrolled on or after April 5, 2021, who met eligibility criteria, consented, and have an evaluable Freenome test result, with confirmed diagnosis from the colonoscopy and best available evidence of histopathology, including central pathology review.

This will be the population used in the analyses of the primary and other endpoints.

5.4. Safety Analysis Set (SAS)

The safety analysis set is defined as enrolled* subjects with a study intervention. The intervention in this study was the attempted blood sample collection. All subjects in the SAS will be evaluated for Adverse Events, and have their demographics characterized in the analysis.

6. Study Objectives and Endpoints

6.1. Diagnostic Accuracy Estimation and Notation

All endpoints are based on groups of disease-positive and disease-negative subjects, with group membership varying as required by the endpoint definitions. Subject disease status is defined in terms of the four Categories listed in Table 3, or in certain cases, in terms of specific Category subtypes. Typical disease status definitions are listed in Table 4. Unless otherwise noted, the negative class for purposes of specificity, negative predictive value and positive predictive value estimation is the combination of Categories 3 and 4.

Table 4 - Disease positive/negative subject groups used in various sensitivity/specificity calculations related to endpoints

Sensitivity endpoint	Specificity endpoint	Disease positive	Disease negative

This document contains confidential, proprietary information and may not be reproduced or disclosed in whole or in part without written authorization from Freenome Holdings, Inc

		Approval Status	Approved
		Effective Date	5-Jan-2024
Document Number	PL-00052	Current Revision	5
Document Title	Clinical Validation of Freenome's Methylation Blood Test for the Early Detection...		
Document Category	Plan		

Sensitivity for CRC	Specificity for non-ACN	Category 1	Categories 3-4
Sensitivity for ACN	Specificity for non-ACN	Categories 1-2	Categories 3-4
Sensitivity for AA	Specificity for non-ACN	Category 2	Categories 3-4
Sensitivity for NAA	Specificity for NEG	Category 3	Category 4
N/A	Specificity for no CS findings	N/A	NEG4.4

Diagnostic accuracy data will be presented in the form of 2 x 2 tables, as shown in Table 5, which will be presented separately for each relevant endpoint.

Table 5 - Contingency table for the FMBT-CRC

FMBT-CRC	Clinical Outcome (CS with Histopathology)	
	Disease Positive	Disease Negative
Test Positive	TP	FP
Test Negative	FN	TN

- Table 5 includes the number of true positives (TP, those who have the disease and test positive), false positives (FP, those who do not have the disease but test positive), false negatives (FN, those have the disease but test negative) and true negatives (TN, those who do not have the disease and test negative).
- From the 2 x 2 contingency table, specificity and sensitivity will be assessed and reported with two-sided exact 95% confidence intervals (Wilson score method).
- Additional performance characteristics will also be presented, e.g., positive and negative predictive values; positive and negative likelihood ratios.

Some of the endpoints estimated as part of this study identify subjects in more detail than the 2 x 2 contingency table presented in Table 5, as shown in Table 6.

This document contains confidential, proprietary information and may not be reproduced or disclosed in whole or in part without written authorization from Freenome Holdings, Inc

		Approval Status	Approved
		Effective Date	5-Jan-2024
Document Number	PL-00052	Current Revision	5
Document Title	Clinical Validation of Freenome's Methylation Blood Test for the Early Detection...		
Document Category	Plan		

Table 6 - Detailed contingency table for the FMBT-CRC

FMBT-CRC	Clinical Outcome (CS with Histopathology)		
	CRC Positive	AA Positive	Non-ACN Negative
Test Positive	TP _{CRC}	TP _{AA}	FP _{non-ACN}
Test Negative	FN _{CRC}	FN _{AA}	TN _{non-ACN}

This study depends on standard performance characteristics for a screening test. The following endpoints will be assessed (primary and secondary endpoints in bold):

- The sensitivity (Sn) or TP rate of the test is defined as TP/(TP + FN). This will be presented for CRC, AA and ACN groups of subjects as follows:
 - $Sn_{CRC} = TP_{CRC}/(TP_{CRC} + FN_{CRC})$
 - $Sn_{AA} = TP_{AA}/(TP_{AA} + FN_{AA})$
 - $Sn_{ACN} = TP_{ACN}/(TP_{ACN} + FN_{ACN})$
- The specificity (Sp) or TN rate of the test is defined as TN/(TN + FP). This will be presented for the non-ACN, NEG, NEG 4.1 through 4.3, and NEG 4.4 (no CS findings) groups of subjects as follows:
 - $Sp_{non-ACN} = TN_{non-ACN}/(TN_{non-ACN} + FP_{non-ACN})$
 - $Sp_{NEG} = TN_{NEG}/(TN_{NEG} + FP_{NEG})$
 - $Sp_{NEG4.1-4.3} = TN_{NEG4.1-4.3}/(TN_{NEG4.1-4.3} + FP_{NEG4.1-4.3})$
 - $Sp_{NEG4.4} = TN_{NEG4.4}/(TN_{NEG4.4} + FP_{NEG4.4})$
- FP rate will be calculated for each specificity as 1-Sp.
- The positive predictive value (PPV) of the test is defined as TP/(TP + FP). This will be presented with respect to CRC, AA and ACN disease-positive definitions.
 - $PPV_{ACN} = TP_{ACN}/(TP_{ACN} + FP_{non-ACN}) = (PLR_{ACN} * Prev_{ACN})/(1 + Prev_{ACN} * (PLR_{ACN} - 1))$

This document contains confidential, proprietary information and may not be reproduced or disclosed in whole or in part without written authorization from Freenome Holdings, Inc

		Approval Status	Approved
		Effective Date	5-Jan-2024
Document Number	PL-00052	Current Revision	5
Document Title	Clinical Validation of Freenome's Methylation Blood Test for the Early Detection...		
Document Category	Plan		

- $PPV_{CRC} = TP_{CRC}/(TP_{ACN} + FP_{non-ACN}) = (PLR_{CRC} * Prev_{CRC})/(1 + Prev_{CRC} * (PLR_{CRC} - 1))$
- $PPV_{AA} = TP_{AA}/(TP_{ACN} + FP_{non-ACN}) = (PLR_{AA} * Prev_{AA})/(1 + Prev_{AA} * (PLR_{AA} - 1))$
- The negative predictive value (NPV) of the test is defined as $TN/(TN + FN)$. This will be presented with respect to the non-ACN disease-negative definition.
 - $NPV_{non-ACN} = TN_{non-ACN} / (TN_{non-ACN} + FN_{ACN}) = (1 - Prev_{ACN}) / (1 + Prev_{ACN} * (NLR_{ACN} - 1))$
- The positive likelihood ratio (PLR) is defined as:
 - $PLR_{ACN} = Sn_{ACN} / (1 - Sp_{non-ACN})$
 - $PLR_{CRC} = Sn_{CRC} / [(TP_{AA} + FP_{non-ACN}) / (N_{AA} + N_{non-ACN})]$
 - $PLR_{AA} = Sn_{AA} / [(TP_{CRC} + FP_{non-ACN}) / (N_{CRC} + N_{non-ACN})]$
- The negative likelihood ratio (NLR) is defined as $(1 - Sn) / Sp$.
 - $NLR_{ACN} = (1 - Sn_{ACN}) / Sp_{non-ACN}$
 - $NLR_{CRC} = (1 - Sn_{CRC}) / [(FN_{AA} + TN_{non-ACN}) / (N_{AA} + N_{non-ACN})]$
 - $NLR_{AA} = (1 - Sn_{AA}) / [FN_{CRC} + TN_{non-ACN}] / (N_{CRC} + N_{non-ACN})$

For Sensitivity and Specificity, confidence intervals (CI) will be calculated using the Wilson score method. For PLR and NLR, the CI for the ratio of two independent proportions will be calculated using the non-iterative Score approach described by Nam (1995) [FDA, 2017]. For PPV and NPV, the CI will be calculated using the CI of the corresponding predictive value (PLR and NLR, respectively), where prevalence is a constant (FDA, 2017).

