The secondary endpoint for AA sensitivity is a two-sided 95% CI based on the observed sensitivity point estimate (Sn_{AA}). The CI will be constructed using the Wilson score method and all FAS subjects identified as AA by CS and best available evidence, including central histopathology. A lower CI bound that exceeds 11.5% corresponds to rejecting the null hypothesis at the one-sided $\alpha = 0.025$ level.

7. Sample Size Justification

The study should include a minimum of 56 evaluable CRC cases meeting the requirements for inclusion in the FAS analysis set for the primary sensitivity endpoint. Assuming a prevalence of 0.30% CRC cases, the minimum number required in the FAS is $56/0.30\% = 19,000$ subjects. Allowing for a 20% unevaluable rate, this gives a required enrollment of 24,000 subjects.

All of the sample size calculations assume the following:

- Power = 90%
- $\alpha = 0.025$

This document contains confidential, proprietary information and may not be reproduced or disclosed in whole or in part without written authorization from Freenome Holdings, Inc

		Approval Status	Approved
		Effective Date	5-Jan-2024
Document Number	PL-00052	Current Revision	5
Document Title	Clinical Validation of Freenome's Methylation Blood Test for the Early Detection...		
Document Category	Plan		

- One-tailed test for greater than the lower bound.
- Statistical power for Specificity_{non-ACN}, Sensitivity_{AA} and Sensitivity_{CRC} were conservatively estimated assuming an exact-binomial distribution, which has greater coverage than Wilson score. Sample size was set such that 90% power was consistently achieved (Chernick 2012).
- The critical value for a given sample size was determined using the Wilson score method.
- From a meta-analysis, the prevalence of CRC is estimated to follow a beta distribution with parameters 3.264 and 816.77; the prevalence of AA is estimated to follow a beta distribution with parameters 34.265, 436.699.
- Given the critical values for Sp_{non-ACN}, Sn_{AA}, and Sn_{CRC}, in addition to the prevalence of AA, CRC, and non-ACN and estimated study size, a distribution of NPV_{non-ACN} and PPV_{ACN} were generated, from which the 2.5th percentile was used for the acceptance criteria.

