7.1. CRC Sensitivity Sample Size Justification

Assumption: Sn_{CRC}≥85.0%, a sample size of 56 CRC achieves at least 90% power to reject the hypothesis of true CRC sensitivity of ≤ 65.0%.

If 56 CRC subjects are tested, then at least 44 need to be positive by the FMBT-CRC to reject H₀. The CI lower bound corresponding to 44/56 is 66.2%.

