7.2. Non-ACN Specificity Sample Size Justification

Assumption: Sp_{non-ACN} ≥ 90.2%, a sample size of 454 achieves at least 90% power to reject the hypothesis of true non-ACN specificity of ≤ 85.0%.

If 454 non-ACN subjects are tested, then at least 401 need to be negative by the FMBT-CRC to reject H₀. The CI lower bound corresponding to 401/454 is 85.0%.

This document contains confidential, proprietary information and may not be reproduced or disclosed in whole or in part without written authorization from Freenome Holdings, Inc

		Approval Status	Approved
		Effective Date	5-Jan-2024
Document Number	PL-00052	Current Revision	5
Document Title	Clinical Validation of Freenome's Methylation Blood Test for the Early Detection...		
Document Category	Plan		

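### The brackets in the SAP 6.1 formula for NLR_AA are misplaced, so the printed expression is not a negative likelihood ratio; the effect is confined to a descriptive measure

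*SAP*

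**What the plan says.** SAP section 6.1 first gives a general rule: "The negative likelihood ratio (NLR) is defined as $(1 - Sn) / Sp". It then lists three versions, for ACN, CRC and AA.

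- For AA: "NLR_{AA} = (1 - Sn_{AA}) / [FN_{CRC} + TN_{non-ACN}] / (N_{CRC} + N_{non-ACN". The quote stops before the last characters. All that follows is the round bracket that closes the total; the square bracket has already closed after the test-negative count.
- For CRC: "NLR_{CRC} = (1 - Sn_{CRC}) / [(FN_{AA} + TN_{non-ACN}) / (N_{AA} + N_{non-ACN". Here the characters after the quote close the total and then the square bracket, so the whole fraction sits inside one bracket.
- The positive counterpart for AA, "PLR_{AA} = Sn_{AA} / [(TP_{CRC} + FP_{non-ACN}) / (N_{CRC} + N_{non-ACN", is built the same way as the CRC formula, and so is PLR_CRC.

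The same section plans confidence intervals for PLR and NLR by the non-iterative score method for a ratio of two independent proportions. It also says that likelihood ratios will be presented. Section 8.5 (Additional Analyses), items 4 and 5, lists NLR among the measures to be analysed by site type, by US versus non-US site and by age group, without saying which NLR.

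**The concern.** A negative likelihood ratio compares two proportions: the share of diseased subjects who test negative, and the share of the comparison group who test negative. For AA the comparison group is CRC plus non-ACN. Its negative share is (FN_CRC + TN_non-ACN) divided by (N_CRC + N_non-ACN).

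The printed NLR_AA never forms that share. It divides a proportion by one count and then by another. The result is smaller than the intended ratio by a factor of the group total squared. It also depends on sample size: at equal test performance, a stratum one-tenth the size would give a value 100 times larger. If the expression were programmed as printed, NLR_AA could not be interpreted, and strata would appear to differ because of their size. The planned score interval could not be applied to it either, because the expression is not a ratio of two proportions.

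**Working it through.** The SAP gives no numerical NLR_AA to reproduce, so the check evaluates both forms at the SAP's planning values.

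**Inputs**

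- FAS size 19,000, from SAP section 7: "the minimum number required in the FAS is $56/0.30\% = 19,000$ subjects". The exact quotient is 56/0.003 = 18,667, so the stated figure is rounded up.
- 56 CRC, section 7: "The study should include a minimum of 56 evaluable CRC cases".
- CRC sensitivity 85.0%, section 7.1: "85.0%, a sample size of 56 CRC achieves at least 90% power".
- Non-ACN specificity 90.2%, section 7.2: "90.2%, a sample size of 454 achieves at least 90% power".
- 1,929 AA at sensitivity 14.0%, section 7.5.

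The stated planning results reproduce. Wilson lower bounds are 66.2% for 44/56, 85.05% for 401/454 and 11.53% for 250/1,929. Exact power is 93.2%, 92.0% and 91.2% for CRC sensitivity, specificity and AA sensitivity, against a stated minimum of 90%.

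**Counts**

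- N_non-ACN = 19,000 − 56 − 1,929 = 17,015
- FN_CRC = 0.15 × 56 = 8.4
- TN_non-ACN = 0.902 × 17,015 = 15,347.5
- FN_CRC + TN_non-ACN = 15,355.9
- N_CRC + N_non-ACN = 56 + 17,015 = 17,071

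**Results**

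- As printed: 0.86 / 15,355.9 / 17,071 = 3.28 × 10⁻⁹
- Corrected: 0.86 / (15,355.9 / 17,071) = 0.86 / 0.8995 = 0.956
- Ratio of the two: 17,071² = 2.9 × 10⁸

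**Consistency check.** Section 6.1 links NPV to NLR for ACN by NPV = (1 − Prev) / (1 + Prev × (NLR − 1)). The same identity should hold for AA. With Prev_AA = 1,929/19,000 = 0.1015, the corrected NLR_AA gives 0.9025. The direct count is 15,355.9 / (15,355.9 + 0.86 × 1,929) = 15,355.9 / 17,014.9 = 0.9025, which agrees. The printed form gives 1.000000, which does not.

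**Range**

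| Setting | Printed | Corrected |
|---|---|---|
| Planning values above | 3.28 × 10⁻⁹ | 0.956 |
| Critical rates (44/56, 250/1,929, 401/454), same group sizes | 3.39 × 10⁻⁹ | 0.988 |
| 57 CRC (0.30% of 19,000) and 1,382 AA (mean 7.28% of the section 7 beta distribution) | 3.08 × 10⁻⁹ | 0.956 |
| Total from 16,000 to 25,000 (assumed range), AA at the beta mean | 4.3 × 10⁻⁹ down to 1.8 × 10⁻⁹ | 0.956 |

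In the last row the corrected value does not move with the total, while the printed one falls with its square.

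**The case against.** The best defence is that the intent is not in doubt. The general definition stands in the same list, three parallel formulas are bracketed correctly, and the interval method needs a proportion in the denominator. The Rev 3 change log adds that these likelihood ratios were revised so that, combined with prevalence, they return the predictive values. A competent programmer would probably write the right code, and a value near 3 × 10⁻⁹ beside an NLR_CRC of ordinary size would draw attention. All of this stands and keeps the point small. It does not make the printed formula correct.

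A bracket lost when the PDF was read by a program cannot be fully excluded. It is unlikely, since the parallel formulas in the same section came through intact, and a look at the source SAP settles it.

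A reader might infer three stronger things that the documents do not support.

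- **That the study would report a near-perfect rule-out for AA.** This needs the slip to be programmed literally and to pass every check. Nothing in the documents makes that likely.
- **That the co-primary NPV is affected.** It is not. NPV_non-ACN is calculated from NLR_ACN, which is written correctly, and section 6.1 presents NPV only for non-ACN. Sections 6.3 and 6.4 make no use of NLR_AA.
- **That the formula divides by the total twice.** It divides once by the test-negative count and once by the total. The total squared is the size of the discrepancy from the intended form, not a description of the printed operation.

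**Conclusion.** The formula is wrong as written and should be corrected, but the consequence is minor. It contradicts the SAP's own definition, the three parallel formulas and the planned interval method. Followed literally, it is too small by a factor of about 2.9 × 10⁸ at the planning values.

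The figure of 0.96 for the corrected form is an illustration built from section 7, not a value that the sponsor planned or stated. It assumes that the planning sensitivities and specificity hold exactly in a FAS of 19,000. The conclusion does not depend on those inputs, because the printed form is of order 10⁻⁹ in every setting tried and the corrected form is between about 0.96 and 0.99. No acceptance criterion, sample size or specified predictive value changes. What is affected is a descriptive measure, and the section 8.5 analyses to the extent that their unspecified NLR includes the AA version.

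**What to change.** In SAP section 6.1, write:

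`NLR_AA = (1 − Sn_AA) / [(FN_CRC + TN_non-ACN) / (N_CRC + N_non-ACN)]`

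This matches the bracketing of NLR_CRC. Confirm against the source SAP file that the misplacement is in the original, and check that the analysis program uses the corrected form; agreement with the NPV identity above is a quick test. The cost is a few bracket characters in the next SAP revision. No data, endpoint or design element changes.

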### 7.3.2 Secondary Endpoints and Analyses

NPV of Freenome's test:

The analysis for Freenome's test NPV for CRC cases ( $NPV_{Non-CRC}$ ) is to determine whether the lower bound of the two-sided CI for the point-estimate of  $NPV_{Non-CRC}$  meets or exceeds the prevalence for Non-CRC in the study population. The analysis for Freenome's test  $NPV_{Non-CRC}$  will be performed using an exact binomial test to compute the two-sided 95% confidence lower bound for the rate among FAS subjects with a test-negative result for those identified without CRC from CS and histopathology.

PPV of Freenome's test:

The analysis for Freenome's test PPV for CRC cases ( $PPV_{CRC}$ ) is to determine whether the lower bound of the two-sided CI for the point-estimate of  $PPV_{CRC}$  meets or exceeds the prevalence of CRC in the study population. The analysis for Freenome's test  $PPV_{CRC}$  will be performed using an exact binomial test to compute the two-sided 95% confidence lower bound for the rate among FAS subjects with a test-positive result for those identified with CRC from CS and histopathology.

Sensitivity of Freenome's test for AA:

The effectiveness analysis for Freenome's test Sn for AA cases ( $Sn_{AA}$ ) is to determine whether the lower bound of the two-sided CI for the point-estimate of  $Sn_{AA}$  meets or exceeds 25%. The analysis for Freenome's test  $Sn_{AA}$  will be performed using an exact binomial test to compute the two-sided 95% confidence lower bound for the percentage of all FAS subjects identified with AA from CS and histopathology with a test-positive result.

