6.3. Study Acceptance Criteria

Primary-Objective Acceptance Criteria

The primary objective of this study is to determine that FMBT-CRC is suitable for clinical use. The primary objective will be evaluated using co-primary endpoints of Sn_{CRC} , $Sp_{non-ACN}$, $NPV_{non-ACN}$, and PPV_{ACN} computed from the FAS data.

Acceptance criterion for CRC sensitivity

- the lower bound of the 95% confidence interval for CRC sensitivity, calculated with Wilson's method, shall be greater than 65.0%

Acceptance criterion for non-ACN specificity

- the lower bound of the 95% confidence interval for non-ACN specificity, calculated with Wilson's method, shall be greater than 85.0%

Acceptance criterion for non-ACN NPV

- the lower bound of the 95% confidence interval for $NPV_{non-ACN} - Prevalence_{non-ACN}$ shall be greater than 0.16%, where $NPV_{non-ACN}$ is calculated with NLR and the observed prevalence (FDA, 2017)

This document contains confidential, proprietary information and may not be reproduced or disclosed in whole or in part without written authorization from Freenome Holdings, Inc

		Approval Status	Approved
		Effective Date	5-Jan-2024
Document Number	PL-00052	Current Revision	5
Document Title	Clinical Validation of Freenome's Methylation Blood Test for the Early Detection...		
Document Category	Plan		

Acceptance criterion for ACN PPV

- the lower bound of the 95% confidence interval for PPV_{ACN} – $Prevalence_{ACN}$ shall be greater than 1.17%, where PPV_{ACN} is calculated with PLR and the observed prevalence (FDA 2017)

For the study to be a success, the acceptance criteria for Sn_{CRC} , $Sp_{non-ACN}$, $NPV_{non-ACN}$ and PPV_{ACN} must all be met.

Secondary-Objective Acceptance criterion

The secondary objective will be evaluated only if all the primary objectives are met. The acceptance criteria must be met to declare the success of the secondary objective.

- The lower bound of the 95% confidence interval for AA sensitivity calculated with Wilson's method shall be greater than 11.5%

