6.4. Study Endpoints

Primary Endpoints

Sensitivity of FMBT-CRC for CRC

The co-primary endpoint for CRC sensitivity is a two-sided 95% CI based on Sn_{CRC} . The CI will be constructed using the Wilson score method and all FAS subjects identified as CRC by CS and best available evidence, including central histopathology. A lower CI bound that exceeds 65.0% corresponds to rejecting the null hypothesis at the one-sided $\alpha = 0.025$ level.

Specificity of FMBT-CRC for non-ACN

The co-primary endpoint for non-ACN specificity is a two-sided 95% CI based on $Sp_{non-ACN}$. The CI will be constructed using the Wilson score method and all FAS subjects identified as non-ACN by CS and best available evidence, including central histopathology. A lower CI bound that exceeds 85.0% corresponds to rejecting the null hypothesis at the one-sided $\alpha = 0.025$ level.

Negative predictive value of FMBT-CRC for non-ACN

This document contains confidential, proprietary information and may not be reproduced or disclosed in whole or in part without written authorization from Freenome Holdings, Inc

		Approval Status	Approved
		Effective Date	5-Jan-2024
Document Number	PL-00052	Current Revision	5
Document Title	Clinical Validation of Freenome's Methylation Blood Test for the Early Detection...		
Document Category	Plan		

The co-primary endpoint for non-ACN NPV is a two-sided 95% CI based on $NPV_{non-ACN} - Prevalence_{non-ACN}$. The CI will be constructed using NLR and the observed non-ACN prevalence (FDA, 2017), all FAS subjects with a negative FMBT-CRC result, and disease status from CS and best available evidence, including central histopathology. A lower CI bound that exceeds 0.16% among FAS subjects corresponds to rejecting the null hypothesis at the one-sided $\alpha = 0.025$ level.

Positive predictive value of FMBT-CRC for ACN

The co-primary endpoint for ACN PPV is a two-sided 95% CI based on $PPV_{ACN} - Prevalence_{ACN}$. The CI will be constructed using the PLR and observed ACN prevalence (FDA, 2017), all FAS subjects with a positive FMBT-CRC result, and disease status from CS and best available evidence, including central histopathology. A lower CI bound that exceeds 1.17% among FAS subjects corresponds to rejecting the null hypothesis at the one-sided $\alpha = 0.025$ level.

Secondary Endpoint

Sensitivity of FMBT-CRC for AA

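### SAP 6.1 holds the observed FAS prevalence constant, so the reported 95% intervals for PPV_CRC and NPV_non-ACN are too narrow for the sampled population; the co-primary criteria are not materially affected

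*SAP*

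**What the plan says.** SAP 6.1 defines PPV for three disease groups ("This will be presented with respect to CRC, AA and ACN disease-positive definitions") and NPV for non-ACN. It gives each as a ratio of counts and as a function of the likelihood ratio and prevalence. For PLR and NLR, "the CI for the ratio of two independent proportions will be calculated using the non-iterative Score approach described by Nam (1995"). For the predictive values, "the CI will be calculated using the CI of the corresponding predictive value (PLR and NLR, respectively), where prevalence is a constant".

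SAP 6.3 and 6.4 identify the prevalence for the co-primary quantities: NPV "is calculated with NLR and the observed prevalence (FDA, 2017"), and for PPV "The CI will be constructed using the PLR and observed ACN prevalence (FDA, 2017"). For PPV_CRC and PPV_AA the word observed does not appear. However, the two forms of each formula in 6.1 agree only at the FAS's own prevalence, so the same reading follows.

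The acceptance criteria in 6.3 apply to the differences NPV_non-ACN minus prevalence and PPV_ACN minus prevalence. SAP 8.5 repeats PPV and NPV by site type (item 4) and age group (item 5), and item 7 recalculates them at U.S. intended-use prevalence. Protocol 7.3.2 planned for PPV an "exact binomial test to compute the two-sided 95% confidence lower bound for the rate among FAS subjects with a test-positive result", and the same kind of bound for NPV. Protocol section 7 says the SAP prevails where the two differ.

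**The concern.** A predictive value depends on two estimated quantities, the likelihood ratio and the prevalence. On the odds scale they multiply: odds(PPV) = PLR × odds(prevalence). An interval that moves the PLR across its confidence limits and leaves prevalence at its point estimate carries only the first source of error. With about 57 cancers in 19,000 subjects, the prevalence of CRC is the less precise of the two.

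The SAP itself treats prevalence as uncertain elsewhere. Section 7 gives it beta distributions when setting the PPV and NPV thresholds, and section 4 describes fluctuations in CRC prevalence during the study. SAP 6.1 then sets that uncertainty to zero in the reported intervals.

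At stake is what readers are told about the meaning of a positive or negative result. Estimating NPV_non-ACN is a co-primary objective in SAP 6.2, and PPV_CRC is presented under 6.1. The subgroup tables in 8.5 items 4 and 5 apply the same rule to smaller case counts.

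**Working it through.** **Inputs.** SAP section 7: CRC prevalence 0.30% and FAS 19,000, so 57 expected cancers; "the prevalence of AA is estimated to follow a beta distribution with parameters 34.265, 436.699", mean 34.265/(34.265 + 436.699) = 7.28%. SAP 7.1, 7.2 and 7.5: Sn_CRC 85%, Sp 90.2%, Sn_AA 14%.

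**Reproducing the plan's own figures.** Wilson lower bounds: 44/56 gives 66.2%, 401/454 gives 85.0%, 250/1,929 gives 11.53%. All three match. 56/0.003 = 18,667, stated as 19,000. 19,000/0.8 = 23,750, stated as 24,000. The documents give no coverage figure for PPV or NPV beyond the nominal 95%.

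**Worked example at near-expected counts.** 57 CRC with 48 positive; 1,382 AA with 193 positive; 17,561 non-ACN with 1,721 positive. Test positives: 48 + 193 + 1,721 = 1,962. Test negatives: 19,000 − 1,962 = 17,038, of which TN = 17,561 − 1,721 = 15,840.

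| Quantity | Estimate | SAP method | Wilson | Width ratio |
|---|---|---|---|---|
| PPV_CRC | 48/1,962 = 2.45% | 2.11 to 2.69% | 1.85 to 3.23% | 0.58/1.38 = 0.42 |
| NPV_non-ACN | 15,840/17,038 = 92.97% | 92.82 to 93.13% | 92.57 to 93.34% | 0.31/0.77 = 0.40 |

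**Where the missing width goes.** On the log-odds scale the variance splits into a likelihood-ratio part, which the SAP keeps, and a prevalence part, which it drops. If r² is the share kept, approximate coverage is P(|Z| < 1.96 r).

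- PPV_CRC: kept (1/48 − 1/57) + (1/1,914 − 1/18,943) = 0.00376; dropped 1/57 + 1/18,943 = 0.01760. r = √(0.00376/0.02136) = 0.42, coverage about 59%.
- NPV_non-ACN: kept (1/1,198 − 1/1,439) + (1/15,840 − 1/17,561) = 0.000146; dropped 1/1,439 + 1/17,561 = 0.000752. r = √(0.000146/0.000898) = 0.40, coverage about 57%.
- PPV_ACN: kept (1/241 − 1/1,439) + (1/1,721 − 1/17,561) = 0.00398; dropped 0.00075. r = 0.92, coverage about 93%.

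**Simulation.** 40,000 cohorts per setting: multinomial disease status, binomial test results, score interval for PLR and NLR (solved by bisection), mapped to PPV or NPV at the observed prevalence and compared with the value at the population prevalence.

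| Quantity | SAP coverage | SAP mean width | Wilson coverage | Wilson mean width |
|---|---|---|---|---|
| PPV_CRC | 57.1% | 0.56 points | 95.2% | 1.38 points |
| NPV_non-ACN | 57.5% | 0.31 points | 95.2% | 0.77 points |
| PPV_ACN | 92.9% | 2.66 points | 95.1% | 2.91 points |

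PPV_AA coverage under the SAP method is 92.9%.

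**Sensitivity of the 57%.**

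| Setting changed | PPV_CRC | NPV_non-ACN |
|---|---|---|
| CRC prevalence 0.398% (SAP beta mean) | 58.1% | 58.4% |
| FAS 16,000 | 56.7% | 56.9% |
| Sampling stopped at 56 cancers | 58.0% | 56.9% |
| SAP critical values (44/56, 250/1,929, 401/454) | 63.4% | 55.5% |
| True Sn_CRC 70% | 71.2% | 56.4% |
| True Sn_CRC 95% | 42.2% | 58.2% |
| AA 10%, Sn_CRC 80%, Sn_AA 12.5%, Sp 91.5% | 62.9% | 53.3% |

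**Two checks that limit the point.** At the SAP's assumptions, PPV_ACN minus prevalence is covered in 94.9% of trials and NPV minus prevalence in 94.7%, with one-sided lower-bound error of 2.7% and 2.8% against a nominal 2.5%. If the target is the predictive value at each study's realised prevalence, coverage is 95.0% for PPV_CRC and 94.9% for NPV.

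**The case against.** The strongest reply is that the SAP declares its convention: prevalence is a constant, so the interval is conditional, and for that target coverage is about 95%. The population target is also open to argument. The study aims for at least 70% of subjects aged 65 to 85, while the intended use is 45 and older, so FAS prevalence partly reflects a chosen age mix. SAP 8.5 items 7 and 8 handle projection to the U.S. population separately. The method is attributed to 2017 FDA guidance, which cannot be consulted here.

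Part of this stands. A clear conditional label would make the intervals correct for what they then claim. But the SAP never says the intervals apply only at the study's own realised prevalence, and its synopsis calls the enrolled subjects a representative sample of the average-risk screening population. A reader will therefore take them as population intervals.

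A reader might infer three stronger things that the documents do not support.

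- *That the co-primary test is invalid.* The criteria in 6.3 are on differences from prevalence, where the prevalence error largely cancels.
- *That a ranked endpoint is misreported.* PPV_CRC is a secondary objective in the protocol, but the SAP prevails and its only secondary objective is Sn_AA. PPV_CRC is a supplementary output. For NPV_non-ACN, the endpoint interval in 6.4 is the difference.
- *That 57% is a fixed property of the method.* For PPV_CRC it depends strongly on true sensitivity.

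Nor is the protocol's method a complete model. Its binomial bound was compared with the study prevalence without a stated allowance for error in that prevalence, and its NPV was for CRC, not non-ACN.

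**Conclusion.** The concern holds as a reporting error of moderate severity. As 95% intervals for the predictive value in the sampled population, those for PPV_CRC and NPV_non-ACN are about 40% of the width they should have. Coverage at the SAP's design assumptions is about 57% for each. Across the settings tried it is 42% to 71% for PPV_CRC and roughly 53% to 59% for NPV_non-ACN, and none comes near 95%. PPV_ACN and PPV_AA lose about two points.

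This rests on two readings: that the constant is the observed FAS prevalence (stated in 6.3 and 6.4, implied by the identities in 6.1), and that the target is the population value. Under the narrower target of the study's realised prevalence there is no shortfall, only a missing label. The success decision does not change on either reading.

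**What to change.** In SAP 6.1, report PPV_CRC, PPV_AA, PPV_ACN and NPV_non-ACN in the FAS with two-sided 95% Wilson intervals on TP/(all test positives) and TN/(all test negatives). Do the same in 8.5 items 4 and 5. Wilson is already the SAP's method for sensitivity and specificity.

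Keep the fixed-prevalence PLR/NLR interval for the difference criteria in 6.3 and for 8.5 item 7, where prevalence is external, and label it as conditional on prevalence.

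Add a note that the Wilson interval is not to be compared with the observed prevalence to judge the difference criterion. The worked example shows why. Observed non-ACN prevalence is 17,561/19,000 = 92.43%. The SAP's lower bound for NPV minus prevalence is 0.39 points, which passes the 0.16% criterion. The Wilson lower bound for NPV lies only 0.15 points above that prevalence and could be misread as a failure.

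The cost is a short SAP edit, a small programming change, wider published intervals, and two differently labelled intervals to explain. No threshold, sample size or success rule changes.
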